#### 6.6 Secondary outcome

 A secondary outcome variable of clinical recurrence of Crohn's disease (defined by a CDAI value of greater than 150 together with a 100 point rise in the CDAI score from baseline), OR the need for anti-inflammatory rescue therapy OR primary surgical intervention will be analysed in the same way as the primary outcome.

The number of patients with each element of this combined endpoint will be summarised separately. For rescue therapy, the number of patients who take each medication type (5 ASAs, corticosteroids, anti-tumour necrosis factor, azathioprine, methotrexate, allopurinol, antibiotics for Crohn's disease, oral nonsteroidal anti-inflammatory drugs) will be tabulated in the Concomitant Medication section. For surgical intervention, the number of surgical interventions per patient will be summarised. These will be classified as primary or secondary. The time to surgery will also be summarised.

a. An informal sensitivity analysis comparing patients who are 'on-drug' versus those who are 'off-drug' at the end of their time in the trial with respect to the secondary endpoint will be presented by means of a Kaplan-Meier plot. No formal statistical testing will be performed.

<sup>2 Postoperative clinical recurrence of Crohn's disease (defined by a Crohn's Disease Activity Index value of greater than 150 together with a 100 point rise in the CDAI score from baseline), together with the need for anti-inflammatory rescue therapy or primary surgical intervention.

- Endoscopic recurrence using both the Rutgeert's and CDEIS scoring system will be summarised by time and treatment group. Colonoscopy results will also be summarised.
- 3. Colonoscopy results at Visit 12 will be compared between the treatment groups using a chi-squared test. CDEIS scores at Visit 12 will be compared between the treatment groups using a t-test.
- 4. Faecal calprotectin results will be summarised by time and treatment group, both as a continuous measure and categorically. The continuous change from baseline to each time point will also be summarised.

The use of faecal calprotectin as a non-invasive marker of clinical recurrence of Crohn's disease will be examined in two ways:

- Levels will be compared descriptively between those with negative (≤ i1) or positive (≥ i2) colonoscopies at 12 and 36 months.
- ii. Time to disease recurrence will be analysed using a Cox proportional hazards model (as detailed in Section 6.5), incorporating calprotectin results as a time dependent covariate, provided there are sufficient outcome events.

Hazard ratios with corresponding 95% confidence interval will be estimated, indicating whether calprotectin levels are surrogate markers of disease recurrence.

5. Thioguanine (TGN) levels of the 6MP drug metabolite samples will be summarised by time and treatment group, both as a continuous measure and categorically following independent blind review. The continuous change from baseline to each time point will also be summarised.

TGN levels of the 6MP drug metabolite samples will also be considered as a time dependant covariate in the Cox proportional hazards analysis of time to disease recurrence (as detailed in 3.ii above). Patients receiving placebo will not be included in this analysis.

- Quality of life will be assessed by the validated indices IBDQ, EQ-5D and SF-36, as follows:
  - a. The values at baseline and each time point, in each of the various subscales of these measures will be summarised (without statistical testing). The change from baseline to each time point will be summarised for IBDQ (average and total) and SF-36 only (physical component score and mental component score).
  - b. Change from baseline in overall IBDQ (average and total) and SF-36 (physical component score and mental component score) indices will be

<sup>3 A negative colonoscopy is defined as a Rutgeert's score of  $\leq$  i1, while a positive colonoscopy is defined as a Rutgeert's score of  $\geq$  i2.

<sup>4 The primary outcome i.e. a Crohn's Disease Activity Index value of greater than 150 together with a 100 point rise in the CDAI score from baseline, together with the need for anti-inflammatory rescue therapy or primary surgical intervention.

modelled using a repeated measures analysis of covariance, fitting terms for treatment, time (visit) and the interaction between treatment and time (visit). Patient and time will be included in the model as random effects.

The estimated treatment effect and 95% confidence intervals will be presented at each timepoint and overall.

c. IBDQ takes precedence over the other Quality of Life scales in terms of clinical importance. In order to take account of missing response data, a sensitivity analysis using multiple imputation techniques may be undertaken for IBDQ only. This will be analysed in the same way as the proposed repeated measures analysis (4b).

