#### 3 Introduction

This document details the criteria to be used for the definition of the analysis populations and the statistical methodology for analysis for the TOPPIC trial, a randomised trial of 6-mercaptopurine versus placebo to prevent recurrence of Crohn's disease following surgical resection. This document has been compiled according to the Edinburgh Clinical Trials Unit (ECTU) standard operating procedure (SOP) "Statistical Analysis Plans" and has been written based on information contained in the study protocol version 13, dated 29 April 2015.

TOPPIC is a multicentre, randomised, parallel-group, placebo-controlled trial. Treatment allocation is a 1:1 ratio. Patients are randomised to either 6-mercaptopurine or matched placebo control. The aim was to recruit 234 patients.

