#### 6.3 Adherence with trial protocol and allocated treatment

No formal statistical testing will be performed. The following will be presented:

- Number and percentage of patients who were ineligible for inclusion in trial (if any it should not have been possible to randomise such patients).
- Numbers of patients who were randomised but never treated.
- Numbers of patients who took trial medication for the full 3 years, and those who stopped early.

For those who stopped early, they will be categorised as:

Primary outcome-related event Other adverse event Blood test result Other reasons

Time to stopping medication will be presented as a Kaplan-Meier plot, split by allocated treatment.

 Prescribed dose will be summarised. Dose at final visit compared with dose at first visit will be summarised as:

> Dose increased Dose stayed the same Dose decreased Trial medication stopped early

- A summary of patients attending and withdrawing at each visit will be presented, together with reasons for withdrawal.
- A listing of patients where the blind was broken early will be presented, including details of allocation, timing and reason for breaking blind, and outcome.

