#### 6.5 Primary Outcome

The primary outcome variable is the timing of postoperative clinical recurrence of Crohn's disease.

For the purposes of the statistical analysis, the date of recognition of clinical recurrence as assessed by the CDAI score will be considered the date of primary outcome provided that anti-inflammatory rescue therapy or primary surgical intervention is initiated as part of the same clinical episode. If there is any doubt that events form part of the same clinical episode, this will be assessed by the CI who will be blinded to the treatment allocation. It is recognised that, in some cases, rescue therapy may have been initiated before the CDAI score reaches the trigger criteria.

The primary outcome will be assessed as follows:

- a. The times, split by treatment group, will be presented using a Kaplan-Meier plot. If distributional assumptions hold, this will be analysed using Cox proportional hazards regression. The effect of treatment allocation will be reported as an adjusted (as detailed in Section 5) hazard ratio with its corresponding 95% confidence interval. Unadjusted results will be presented as a secondary analysis.
- b. Length of patient follow-up will be summarised, together with a summary of the number followed for 3 years or having a recurrence.

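### The on-drug versus off-drug Kaplan-Meier plot groups patients by a status that the endpoint can cause, so it cannot be interpreted and is not a sensitivity analysis of the randomised comparison

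*SAP*

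**What the plan says.** Item 1a of SAP section 6.6 plans a sensitivity analysis, described as informal, whose contrast is set out as "comparing patients who are 'on-drug' versus those who are 'off-drug' at the end of their time in the trial". The display is a pair of Kaplan-Meier curves, and the SAP states that no test will accompany them. The endpoint is the composite defined at the start of section 6.6: recurrence on the CDAI criterion, or rescue therapy, or primary surgery.

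Section 6.3 will report "Numbers of patients who took trial medication for the full 3 years, and those who stopped early". It classifies early stops into four reasons, the first being "Primary outcome-related event". The footnote to that category defines the event as CDAI recurrence in combination with rescue therapy or primary surgery.

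Section 6.5(b) summarises length of follow-up "together with a summary of the number followed for 3 years or having a recurrence".

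For this plot the SAP gives no landmark time, no time-dependent definition of drug status, no censoring at stopping and no rule for a stop that the event itself brings about. It does not say whether on-drug includes placebo tablets, or whether the curves are split by randomised arm.

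**The concern.** A Kaplan-Meier curve from time zero needs groups that are known at time zero. Here the group is a later status, and two mechanisms tie it to the outcome.

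- **The event can cause the status.** A patient who has the event and stops medication because of it moves to off-drug and takes the event along. This raises apparent risk in the off-drug group.
- **Stopping takes event-free time.** If status is read at the event, a patient who stopped earlier for another reason must have been event-free until then, while a patient with an early event had little time to stop. This lowers apparent risk in the off-drug group.

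The balance between the two has nothing to do with what 6-MP does. The analysis is labelled a sensitivity analysis, but it does not compare the groups as randomised, so it cannot show whether the ITT result is robust. Leaving out a p-value does not change the shape of the curves that a reader will see.

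**Working it through.** The SAP gives no event rate, stopping rate or effect size for this plot, so there is no stated figure to reproduce. The check asks what the plot would show if drug status had no effect on the endpoint.

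**1. Link between endpoint and status.** The stopping category in section 6.3 requires CDAI recurrence *and* (rescue or surgery). The plotted endpoint requires CDAI recurrence *or* rescue *or* surgery. The first implies the second, so every patient in that stopping category has had the plotted event. The reverse does not hold: a patient may meet the composite on one component and remain on drug.

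**2. Inputs.** From the SAP: 3 years of treatment and follow-up. Assumed, not in the SAP: 3-year event risk 40%; other-cause stopping hazard μ = 0.15 per year, independent of the event; a share p of events occurring on drug that leave the patient off drug.

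Event hazard λ = −ln(0.6)/3 = 0.1703. Sum s = λ + μ = 0.3203.

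**3. Proportions of patients, with status read at the event or at 3 years, whichever comes first**

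- Event while still on drug: (λ/s)(1 − e^(−3s)) = 0.5317 × 0.6174 = 0.3283
- Event after an other-cause stop: 0.4 − 0.3283 = 0.0717
- No event, never stopped: e^(−3s) = 0.3826
- No event, stopped: 0.6 − 0.3826 = 0.2174

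**4. Person-years per patient randomised**

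- Events on drug: (λ/s²)[1 − e^(−3s)(1 + 3s)] = 0.4147
- All events: (1/λ)[1 − 0.6(1 + 3λ)] = 0.5491, so events after stopping contribute 0.5491 − 0.4147 = 0.1344
- Patients without an event contribute 3 years each: 3 × 0.3826 = 1.1477 (on) and 3 × 0.2174 = 0.6523 (off)

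**5. Null rate ratio**

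- Off rate = (0.0717 + 0.3283p) / (0.1344 + 0.4147p + 0.6523)
- On rate = 0.3283(1 − p) / (0.4147(1 − p) + 1.1477)

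| p | Off: share with event | On: share with event | Off rate | On rate | Off/on ratio |
|---|---|---|---|---|---|
| 0 | 25% | 46% | 0.091 | 0.210 | 0.43 |
| 0.25 | 41% | 39% | 0.173 | 0.169 | 1.02 |
| 0.50 | 52% | 30% | 0.237 | 0.121 | 1.96 |
| 0.80 | 61% | 15% | 0.299 | 0.053 | 5.60 |

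**6. Other reading: status at 3 years, with follow-up continuing after the event.** Other-cause stopping by 3 years is then 1 − e^(−0.45) = 0.362, whether or not the patient has had the event. The null ratios are 1.00, 1.64, 2.75 and 7.36 for p = 0, 0.25, 0.5 and 0.8. The event-free-time effect disappears, and the effect of event-driven stopping remains.

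**7. How visible this would be at the planned size.** "The aim was to recruit 234 patients". Null trials of 234 patients were simulated, 1,500 per scenario, with 3-year event risk and 3-year other-cause stopping each set at 20% or 40%. With p = 0.5, a log-rank test would give p < 0.05 in 68% to 100% of trials (status at the event) or 96% to 100% (status at 3 years). No such test is planned; these figures only show how clearly the curves would part.

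**8. Check of a fix.** Attribute each event to the status held just before it, and split person-time at the stop. On-drug person-years are (1 − e^(−3s))/s = 1.9278. Off-drug person-years are 0.4/λ − 1.9278 = 0.4213. The rates are 0.3283/1.9278 = 0.170 and 0.0717/0.4213 = 0.170, a ratio of 1.00. In the simulated trials of 234 it was 0.99 to 1.00.

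**The case against.** The strongest reply is that the plot is declared informal, carries no test, and supports no estimate or conclusion. The primary and secondary endpoints keep their ITT Cox analyses. This stands, and it limits the severity.

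Second, the link in section 6.3 is looser than it may look. That section sorts reasons among patients who stopped; it does not say that an event leads to stopping. Its category also refers to the primary definition, whereas the plot uses the broader composite. This stands in part: the SAP shows that the endpoint *can* cause off-drug status, not that it always does.

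Third, a reader might infer that the plot is bound to show a large false advantage for staying on drug. The SAP does not support that. The size and direction depend on the share of events that leave patients off drug, which it does not give, and on when status is read, which it does not fix. With a quarter of events doing so and status read at the event, the two biases nearly cancel (1.02). With none, the curves favour off-drug (0.43), or coincide if status is read at 3 years.

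This third objection limits what can be said about direction, but it does not rescue the plot. A figure whose appearance under no effect runs from 0.43 to above 5 according to an unstated quantity cannot inform a reader.

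**Conclusion.** The concern holds in a conditional form. The grouping is post-baseline and can be caused by the endpoint, so the curves can separate spuriously in either direction when drug status has no effect. Under the stated assumptions the null off/on rate ratio runs from 0.43 to 5.60 with status read at the event, and from 1.00 to 7.36 with status read at 3 years, as the share of events leaving patients off drug goes from 0% to 80%. These figures rest on constant hazards, on other-cause stopping that is independent of the event, and on event and stopping rates that the SAP does not give. They illustrate the problem and do not forecast this trial's plot.

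The plot is uninterpretable and should not be called a sensitivity analysis of the randomised comparison. It would also be wrong to conclude that the main results are compromised, because the ITT primary and secondary analyses do not depend on it. Severity is minor to moderate.

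**What to change.** Replace item 1a with one of the following.

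1. **A comparison of the randomised arms** on the secondary endpoint, censoring at permanent stopping of trial medication for reasons other than the endpoint. A stop triggered by the endpoint is not a censoring event. Inverse-probability-of-censoring weights are optional; they need a model for stopping, which may be more than 234 patients justify.
2. **Drug status as a time-dependent covariate within randomised arm**, attributing each event to the status held just before the event or before the stop that it triggered. The rule for recognising such a stop should be fixed before unblinding, because section 6.5 accepts that rescue therapy may start before the CDAI criterion is met.

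Under either option, state the assumption that other-cause stopping is unrelated to prognosis given the covariates, and define on-drug for patients allocated placebo. The first option keeps the randomised contrast and better fits the label of a sensitivity analysis.

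The cost is a change of SAP wording and a little programming. Times to stopping are already needed for the plot in section 6.3, and time-dependent Cox covariates are already planned for calprotectin and TGN. The downside is that the assumption about other-cause stopping cannot be tested from the data.

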#### Example 1. Data presentation for categorical data

#### Example 2.Data presentation for continuous data

Parameter	Timepoint / visit	Statistic/ category	6-MP	Placebo	Overall
			N=xx	N=xx	N=xx
Parameter	Timepoint x	Mean	XX	XX	xx
		Median	xx	xx	xx
		SD	xx	xx	xx
		Q1, Q3	xx, xx	xx, xx	xx, xx
		Min, Max	xx, xx	XX, XX	xx, xx
		n	xx	xx	xx

All applicable statistical tests will be 2-sided and will be performed using a 5% significance level. 95% (2-sided) confidence intervals (CIs) will be presented. All analyses are seeking to show a difference, rather than equivalence or non-inferiority.

Where there is missing data for an outcome variable, in the first instance, those records will be removed from any formal statistical analysis relating to that outcome variable, unless otherwise specified. In tabulations, numbers of missing observations will be provided, but percentages will not include them.

The main statistical analyses for primary and secondary outcomes will be adjusted for centre and smoking status (from randomisation stratification) and baseline values of 'Previous treatment with 6MP' and 'Previous treatment with Azathioprine' following note from DMC in January 2013. Results of unadjusted statistical analyses will also be presented.

Distributional assumptions underlying the statistical analyses will be assessed by visual inspection of residual plots. Normality will be examined by normal probability plots. If the distributional assumptions for the parametric approach are not satisfied, further data transformation (to alleviate substantial skewness (i.e. normalizing) or to stabilise the variance), or other suitable methods will be considered. This will be documented in the statistical results report together with the reasoning supporting the action taken, if applicable.

All analyses and data manipulations will be carried out using SAS [1].

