#### 6.8 Subgroup analyses

The following subgroup analyses are planned:

- i. Patients who are thiopurine naïve (have had previous treatment with either 6MP or Azathioprine)
- ii. Patients who have had previous treatment with Infliximab or Methotrexate
- iii. Patients who have had previous surgery
- iv. Smoking status
- v. Duration of disease ( $\leq 1$  year, > 1 year)
- vi. Age at diagnosis (≤40 years, > 40 years)

The primary and secondary outcomes defining clinical recurrence of Crohn's disease will be analysed for these subgroups. The interaction between subgroup and treatment will be included in the Cox regression model (as described in Section 6.5) to determine if the treatment effect differs by subgroup.

Endoscopic recurrence as defined by Rutgeert's score and the CDEIS score will be summarised and analysed separately for these subgroups in line with the methods described in Section 6.6. Similarly to the subgroup analyses of the primary and secondary outcomes, the interaction between subgroup and treatment will be assessed to determine if the treatment effect differs by subgroup.

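### Section 5 calls for a covariate-adjusted main analysis, but none is named for the endoscopic outcomes, nor any model for the interaction that Section 6.8 requires of them

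*SAP*

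**What the plan says.** Section 5 sets a general rule: "The main statistical analyses for primary and secondary outcomes will be adjusted for centre and smoking status (from randomisation stratification". The sentence goes on to add previous treatment with 6MP and with azathioprine. The next sentence gives the other analyses a supporting place: "Results of unadjusted statistical analyses will also be presented". No secondary outcome is exempted.

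Section 6.6, headed as the secondary outcome section, covers the endoscopic outcomes in item 3: "Colonoscopy results at Visit 12 will be compared between the treatment groups using a chi-squared test", and "CDEIS scores at Visit 12 will be compared between the treatment groups using a t-test". A footnote defines a positive colonoscopy as a Rutgeert's score of i2 or more. No adjusted counterpart follows.

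Section 6.8 lists six subgroups. For the clinical recurrence outcomes it names the model: "The interaction between subgroup and treatment will be included in the Cox regression model". For endoscopy it says "Endoscopic recurrence as defined by Rutgeert's score and the CDEIS score will be summarised and analysed separately for these subgroups", using the Section 6.6 methods. It then adds that "the interaction between subgroup and treatment will be assessed to determine if the treatment effect differs by subgroup", without naming a model.

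**The concern.** A chi-squared test on a 2x2 table and a two-sample t-test have no place for centre, smoking or prior thiopurine treatment. An analyst who follows item 3 as written leaves out the stratification factors and departs from Section 5. An analyst who follows Section 5 has to choose a model, a way of handling centre and, for colonoscopy, an effect measure, because item 3 supplies none of these.

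The same gap reappears in Section 6.8. The plan wants to know whether the treatment effect on endoscopic findings differs by subgroup, but the only methods it points to for these outcomes compare two arms and nothing else.

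**Working it through.** **1. Between-arm comparisons side by side**

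| Outcome | Named method | Can it carry the Section 5 covariates? | Interaction model named in 6.8? |
|---|---|---|---|
| Primary (6.5) | Cox, adjusted as in Section 5 | Yes, stated | Yes, Cox |
| Composite clinical recurrence (6.6, first item) | Same as primary | Yes, inherited | Yes, Cox |
| IBDQ and SF-36 (6.6) | Repeated measures analysis of covariance | Yes, terms can be added | Not asked for |
| Positive colonoscopy, Visit 12 (6.6 item 3) | Chi-squared | No | No |
| CDEIS, Visit 12 (6.6 item 3) | t-test | No | No |

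Only the two endoscopic rows have a method that cannot follow the Section 5 rule.

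**2. What an interaction needs**

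With treatment T and subgroup S, the model for positive colonoscopy is logit(p) = a + bT + cS + d(T x S), and the interaction is the test of d = 0. For CDEIS the same right-hand side applies with the mean score on the left. The Section 6.6 tests, run separately in each subgroup, address b in one subgroup and b + d in the other, but do not test d. One could contrast two subgroup estimates by hand, but the plan describes no such step. The number of interactions without a method is 6 subgroups x 2 outcomes = 12.

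**3. How much adjustment would gain**

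The SAP gives no event rates, covariate effects or power for endoscopy, so there is no figure to reproduce. What follows is an illustration for the binary outcome only.

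- From the SAP: 234 patients planned, 1:1, so 234 / 2 = 117 per arm; two-sided 5% level.
- Assumed: every patient scoped; 30% smokers, balanced between arms; a common odds ratio of 0.45; the control rates in the table.
- Compared: the Pearson chi-squared test against a Cochran-Mantel-Haenszel test stratified by smoking alone, with 40,000 simulated trials per setting.

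| Control rate, smokers / non-smokers | Power, unadjusted | Power, stratified | Difference (points) | Type I error, unadjusted | Type I error, stratified |
|---|---|---|---|---|---|
| 60% / 40% | 81.1% | 81.7% | 0.6 | 5.2% | 5.1% |
| 70% / 40% | 80.1% | 81.4% | 1.3 | 5.0% | 5.1% |
| 80% / 30% (extreme) | 64.3% | 73.5% | 9.2 | 3.3% | 5.1% |

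The simulation error on a 5% rate is about sqrt(0.05 x 0.95 / 40,000) = 0.0011, or 0.1 point. In the first two settings the type I errors are therefore essentially nominal. A clear loss appears only when smoking is extremely prognostic. Centre and prior treatment were not modelled.

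**The case against.** The best defence is that the chi-squared and t-tests are simply the unadjusted results that Section 5 allows. Section 5 ranks the analyses, and item 3 never calls its tests the main ones. This stands as far as it goes: a reader might infer two rival main analyses, with the result open to choice after unblinding, and the text does not show that. But on this reading the adjusted main analysis is named nowhere.

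A second defence is scope. Section 6.8 speaks of the primary and secondary outcomes defining clinical recurrence and handles endoscopy apart from them. The heading of 6.6 is singular. The protocol text reproduced in Section 4 states the covariates for the primary analysis only. Item 3 could therefore be a deliberate exception. That is arguable, but endoscopy sits inside Section 6.6 and Section 5 states no exception. Even if this reading is right, the interaction still has no model.

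Third, a reader might infer that subgroup claims would rest on comparing separate p-values. The plan does not say so. The Section 6.6 methods govern the separate subgroup analyses, and a different sentence asks for an interaction, by analogy with the clinical outcomes. The intention is sound; only the model is missing.

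Finally, where the unadjusted test is affected it is conservative, so it does not create false positives. That also stands.

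**Conclusion.** The point holds as incomplete specification. The adjusted main analysis that Section 5 calls for is missing for Visit 12 colonoscopy and CDEIS, and 12 interaction assessments in Section 6.8 have no named method. This rests on the text and on what the two tests can do, not on any assumed figure. It does assume that Section 5 means what it says about secondary outcomes; the interaction gap does not depend on that.

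The weight is moderate. These are secondary outcomes; the primary and composite analyses are adjusted and have an interaction model.

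Efficiency is a minor argument. It is tempting to convert the missing adjustment into extra patients with 1/(1 - R²) - 1, but the SAP says nothing about R², and the formula belongs to a linear model, so it does not apply to the chi-squared comparison. The gain from correcting the plan is consistency with Section 5, a test that respects the stratification, and a valid interaction test.

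**What to change.** Reword Section 6.6 item 3 and the endoscopic paragraph of Section 6.8 as follows.

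- **Positive colonoscopy (i2 or more) at Visit 12.** Main analysis: logistic regression with treatment, smoking status, previous 6MP, previous azathioprine and centre, reporting an adjusted odds ratio with 95% CI.
- **CDEIS at Visit 12.** Main analysis: linear model with the same covariates, reporting an adjusted mean difference with 95% CI. The residual checks already in Section 5 apply.
- **Centre.** Fix one rule for small centres in advance, for example centre as a random effect in both models.
- **Section 6.8.** Add subgroup and subgroup-by-treatment terms to these two models and report the interaction estimate with its 95% CI. Where the subgroup is already a covariate (smoking) or is built from covariates (thiopurine history), do not enter the same information twice.
- **Simple tests.** Keep the chi-squared and t-tests, labelled as the unadjusted supportive results.

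The cost is a few lines of SAP text and some model statements. Section 6.2 already lists centre, smoking status and prior treatment among the baseline data, so no new data are needed. The downside is a little more modelling and an odds ratio that is conditional on the covariates. The primary analysis does not change.

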#### 4 Statistical Methods Section from the Protocol

The primary outcome variable is postoperative recurrence of Crohn's Disease and it's timing if it recurs. Analysis will be by intention-to-treat and will be based on the application of Cox proportional hazards model. The primary analysis will include terms for the treatment, the variables on which the randomisation was stratified and adjusted for baseline values of previous treatment with 6MP and previous treatment with Azathioprine.

The quality of life variables will be analysed using a repeated measures analysis of covariance to evaluate treatment and treatment by time interactions.

The use of faecal calprotectin as a non-invasive marker of disease recurrence will be examined in two ways. It will be firstly considered as a time dependent covariate in the Cox proportional hazards model described above. Secondly, levels will be compared descriptively between those with negative or positive colonoscopies at 12 and 36 months. Similarly, 6MP drug metabolite levels will be also considered as a time dependent covariate in the Cox proportional hazards model.

Exploratory analyses will investigate the inclusion of the clinical, genetic and serological markers in the model. The models will be used to develop a simple scoring system to predict the risk of recurrence. The sample size will be too small to use a split sample approach to validate the prediction, but the use of a simple scoring system will mitigate to some degree the more extreme effects of using observed regression coefficients to define the risk. During the period after trial recruitment, data from new patients will provide limited short-term validation of the predictions.

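### A hazard ratio for time-dependent calprotectin can show association with clinical recurrence, but not that calprotectin is a surrogate, as SAP Section 6.6 item 4.ii says it will

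*SAP*

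**What the plan says.** The aim is given twice. The protocol text reproduced in SAP Section 4 says "The use of faecal calprotectin as a non-invasive marker of disease recurrence will be examined in two ways". Section 6.6, item 4, repeats the aim for the primary outcome definition: "The use of faecal calprotectin as a non-invasive marker of clinical recurrence of Crohn's disease". Neither sentence speaks of surrogacy.

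Two analyses serve this aim in Section 6.6:

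- Item 4.i compares calprotectin with colonoscopy: "Levels will be compared descriptively between those with negative (≤ i1) or positive (≥ i2) colonoscopies at 12 and 36 months".
- Item 4.ii takes the Cox model of Section 6.5, "incorporating calprotectin results as a time dependent covariate, provided there are sufficient outcome events". It then states what the result is for: "Hazard ratios with corresponding 95% confidence interval will be estimated, indicating whether calprotectin levels are surrogate markers of disease recurrence".

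Calprotectin and its change from baseline are also summarised by time and treatment group, with no test between groups. The underlying Cox model contains treatment: "The primary analysis will include terms for the treatment, the variables on which the randomisation was stratified", plus previous 6MP and previous azathioprine.

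**The concern.** Item 4.ii fixes in advance how a result will be read, and that reading goes beyond what the model estimates. The hazard ratio for a time-dependent marker compares the recurrence hazard of patients at different current marker levels, given treatment and the other covariates. It answers whether calprotectin and recurrence go together. Surrogacy is a different question: whether what treatment does to calprotectin tells us what treatment does to recurrence.

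A report that followed the sentence could present an ordinary association as evidence of surrogacy. Meanwhile the question the trial did set, how well calprotectin serves as a non-invasive marker, would rest on a hazard ratio and a descriptive table. Neither measures how well calprotectin separates patients with recurrence from those without.

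**Working it through.** The SAP gives no figure on this point, so there is nothing to reproduce. The check is a reading of the text, with two illustrations on assumed inputs.

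**Step 1: what surrogacy would need, against what is planned**

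| Needed | Planned in the SAP |
|---|---|
| Estimated treatment effect on calprotectin | Summaries by group only (6.6, item 4) |
| Treatment hazard ratio with and without calprotectin, compared | Both models exist; no comparison is specified |
| A criterion, such as proportion of treatment effect explained | None |
| Marker associated with recurrence | Yes (6.6, item 4.ii) |

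Only the last row is addressed, and it is not sufficient alone.

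**Step 2: can a non-surrogate give a clear hazard ratio?**

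From the SAP: 234 patients, 1:1 allocation, two-sided 5% level, three years of treatment. Assumed: a baseline hazard of 0.006 per month; a latent severity U (SD 1) with log hazard ratio 0.9; a marker equal to 0.8U plus noise of SD 0.6, updated every 6 months. The marker SD within an arm is √(0.64 + 0.36) = 1, so the hazard ratio per unit is per SD. There were 300 replicates per scenario.

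- Scenario A: treatment halves the hazard but does not act on the marker.
- Scenario B: treatment lowers the marker by 0.8 but has no effect on recurrence.

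| | A | B |
|---|---|---|
| Mean events | 45 | 57 |
| Marker hazard ratio per SD | 2.03 | 1.98 |
| Replicates with marker p < 0.05 | 99.7% | 99.3% |
| Treatment hazard ratio, marker omitted | 0.52 | 1.02 |
| Treatment hazard ratio, marker included | 0.51 | 1.76 |

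In A the proportion of the log treatment hazard ratio explained is 1 − ln 0.51/ln 0.52 = 1 − 0.673/0.654 = −0.03, which is none. In B the fall in the marker would suggest a benefit that does not exist. The marker hazard ratio is almost the same in both, so it cannot tell a reader about surrogacy.

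**Step 3: does a clear hazard ratio imply good discrimination?**

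Take a hazard ratio of 1.5 per SD, with z ≈ ln(HR) × √events and ln 1.5 = 0.405. The number of events is not in the SAP, so a range is assumed:

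- 30 events: 0.405 × 5.48 = 2.22, p ≈ 0.03
- 45 events: 0.405 × 6.71 = 2.72, p ≈ 0.007
- 60 events: 0.405 × 7.75 = 3.14, p ≈ 0.002

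An equal-variance binormal approximation, treating the log hazard ratio as the standardised separation, gives AUC = Φ(ln HR/√2). For 1.5 this is Φ(0.287) = 0.61; for 2.0 it is Φ(0.490) = 0.69. The conversion is rough for a time-updated covariate. It shows only that a clearly significant hazard ratio can sit beside an AUC not far above 0.5, so discrimination has to be measured directly.

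**The case against.** The best defence is that surrogate is used loosely. The sentence stands under an aim that speaks only of a non-invasive marker, and a time-dependent Cox model is a reasonable way to study such a marker. The SAP sets no rule that p < 0.05 establishes a surrogate. Treatment is in the model, so a treatment hazard ratio adjusted for calprotectin could be set beside the primary one. Adding discrimination measures goes beyond the descriptive comparison that the protocol text prescribes. All of this is fair and limits the weight of the point. It does not rescue the sentence, which states an inference that the analysis cannot support and which goes beyond the plan's own aim. The possible comparison of treatment hazard ratios is not specified, and one trial of this size could give only weak evidence that way.

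Three stronger readings are tempting, and the document does not support them:

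- A reader might infer that calprotectin is to replace colonoscopy. The SAP never proposes this, and the outcome in item 4.ii is clinical recurrence, not endoscopic.
- A reader might infer that samples taken when recurrence is recognised inflate the hazard ratio. For a marker of recurrence, a concurrent sample is relevant information. The sampling schedule may be in the protocol, and no inflation has been quantified.
- A reader might infer that a log scale is required. Cox regression makes no distributional assumption about covariates, Section 5 provides for transformation, and Section 6.6 also summarises calprotectin in categories.

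**Conclusion.** The point holds for the interpretation: the planned hazard ratio supports a statement about association with clinical recurrence and no statement about surrogacy. That conclusion follows from the text and does not depend on the simulation, whose event rates and marker effects are assumptions. The AUC figures rest on assumed event numbers and a rough approximation, and no threshold for a useful AUC is claimed.

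The issue is minor. It concerns one secondary analysis, itself conditional on sufficient events, and does not affect the primary result. It is still worth correcting, because the sentence decides in advance what the trial will say about calprotectin.

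**What to change.** In Section 6.6, item 4.ii, end the sentence after the hazard ratios and confidence intervals with: *describing the association between calprotectin level and clinical recurrence; this will not be interpreted as evidence of surrogacy*. If surrogacy is really intended, its analysis and criteria would have to be specified instead.

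In item 4.i, keep the descriptive comparison and add, at 12 and 36 months, the AUC of calprotectin against a positive colonoscopy (i2 or more, as the SAP already defines it). Add sensitivity and specificity at the calprotectin categories used for the summaries, all with 95% confidence intervals. State the category cut-offs before the analysis.

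Omitting samples taken at the visit where recurrence was recognised could at most be a sensitivity analysis, since it turns a question about a concurrent marker into one about prediction.

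The cost is one changed clause and a small amount of extra analysis on calprotectin and colonoscopy data already collected.
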